The duration of corticosteroid treatment, in months, will be calculated as (Day 1 – Date on which the patient started corticosteroid treatment + 1)/30.4375.

Corticosteroid Schedule

Corticosteroid schedules will include:

- Continuous (daily)
- Intermittent (includes all dosing schedules that do not require the patient to take at least one dose per day)

Non-Ambulatory Status and Loss of Ambulation (LOA)

The non-ambulatory status will be considered as “Yes” if all 3 conditions below are met:

- NSAA walk subscore as “0” (unable to achieve goal independently) on 2 consecutive days within a visit or NSAA was not done due to reason related to non-ambulation
- 6-minute walk test was not done with any reason related to permanent non-ambulation
- No later data showing this patient is still ambulatory. This is not required if non-ambulatory status occurs at the time of early withdrawal, or at the end of Week 96 assessment.

Note, when the NSAA or 6MWT is “Not Done” and the patient meets the non-ambulatory requirements above, a query will be issued to sites to confirm the permanence of non-ambulatory status. Prior to final database lock, the results of queries will be reviewed by Medical Director and Data Management and provided as documentation for non-ambulatory status determination.

Time to LOA is defined as the time from the initiation of eteplirsen for eteplirsen-treated patients, or Week 1 visit for untreated control patients to the first time of permanent non-ambulation. Patients who do not lose ambulation at the time of early withdrawal, or at the end of Week 96 assessment, whichever is earlier, the patient will be censored at the last time at which the patient is determined to be ambulatory.

NSAA and Total Score

The NSAA is a clinician-administered scale specifically designed for DMD patients that rates patient performance on various functional activities. Patients will be asked to perform 17 different functional activities including: stand, walk, stand up from chair, stand on one leg - right, stand on one leg - left, climb box step - right, climb box step - left, descend box step - right, descend box step - left, lift head, get to standing, rise from floor, stand on heels, jump, hop right leg, hop left leg, run 10 meters. Patients will be graded as follows

- 2 = achieves goal without any assistance;
- 1 = modified method but achieves goal independent of physical assistance from another person; and
- 0 = unable to achieve goal independently.

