A total score is derived by summing the scores for all the individual items. The total score can range from 0 (if all the activities are failed) to 34 (if all the activities are achieved). All items should be tested without thoracic braces or leg orthoses. The scale is generally completed in a maximum of 15 minutes.

Ability to Rise Independently from the Floor

The ability to rise independently from the floor (without external support) is indicated by a NSAA subscore greater than 0 (unable to achieve goal independently). To be considered as loss of ability to rise independently for any visit, the NSAA rise from floor subscore has to be zero on 2 consecutive days within a visit or NSAA missing due to reasons related to not able to accomplish the task.

The permanent loss of ability to rise independently from the floor to a patient is considered to have occurred at a specific visit if this visit as well as all subsequent visits, if any, all showed the loss of ability to rise independently from the floor.

[figure not shown]
For patients who were able to rise at baseline, time to the permanent loss of ability to rise independently from the floor is defined as the time from the initiation of eteplirsen for eteplirsen-treated patients, or Week 1 visit for untreated control patients to the first time of permanent loss of ability to rise independently; patients who do not experience permanent loss of ability to rise independently from the floor at the time of early withdrawal, or at the end of Week 96 assessment, whichever is earlier, the patient will be censored at the last time at which the patient is determined to be able to rise independently.

FVC% predicted, CCI

FVC% predicted will be calculated using the prediction equations described by Hankinson (Hankinson et al, (1999 [1]) based on patient's age, and height as following:

FVC% predicted = $100 * FVC / (b0 + b1 * \text{age} + b2 * \text{age}^2 + b3 * \text{height}^2)$, where b0, b1, b2, and b3 are coefficients).

CCI

Calculated Height

Calculated height will be used based on the following formula:

$$\text{Height (cm)} = 4.605U + 1.308A + 28.003$$

where U is the length of the ulna measured by using an anthropometer or calipers, and A is the patient's age in years.

CCI

C [REDACTED]
C [REDACTED]
I [REDACTED]
[REDACTED]
[REDACTED]
[REDACTED]

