7.8. Efficacy Analyses

For any efficacy assessment that is taken on 2 consecutive days within a visit (ie, 6MWT, NSAA items and total score, FVC % predicted), the average value will be used. If the assessment is taken or available only on 1 day, then the value on that day will be used. A value that is marked as invalid or not completed successfully on the eCRF will be considered a missing value.

Analyses of the primary and secondary efficacy endpoints will be performed separately on the primary efficacy set, the efficacy set, and the subset of patients with Baseline 6MWT distance >450 meters.

Due to the high dropout rate in the untreated group, comparisons between the eteplirsen-treated group and the untreated control group will not be meaningful. Therefore, only summaries by treatment group will be presented.

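### Permanent loss of rise must be shown again at every later visit, so a later visit that tells us nothing can delay or erase a loss already observed (SAP 6.7)

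*SAP*

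**What the plan says.** SAP 6.7 builds the endpoint in three steps.

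- **Visit-level loss.** There are two routes. The first is a score rule: "the NSAA rise from floor subscore has to be zero on 2 consecutive days within a visit". The second covers a test that was not obtained: "NSAA missing due to reasons related to not able to accomplish the task". Ability "is indicated by a NSAA subscore greater than 0".
- **Permanence.** Loss is dated at a visit only if "this visit as well as all subsequent visits, if any, all showed the loss of ability to rise independently from the floor".
- **Censoring.** Without permanent loss, "the patient will be censored at the last time at which the patient is determined to be able to rise independently".

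Two other rules bear on this. SAP 7.8 covers assessments done on two consecutive days and names NSAA items among them: "If the assessment is taken or available only on 1 day, then the value on that day will be used". The loss-of-ambulation (LOA) definition, also in SAP 6.7, asks only that no later data show the boy still walking, and waives even that at early withdrawal or at Week 96.

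SAP 7.8.2 reports Kaplan-Meier percentages still able at Weeks 12, 24, 36, 48, 72 and 96, plus medians. SAP 7.8 limits the output to summaries by group.

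**The concern.** The permanence rule asks each later visit to show loss, when what matters is that no later visit shows ability. Two kinds of later visit do neither: NSAA missing for a reason unrelated to the task, and a zero on the only day tested. On the literal wording, both count against a loss already documented by zeros on two days.

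A boy seen unable to rise at several visits could then be reported as losing the ability later than he did, or as censored while able. Only boys who have lost the ability can be moved this way, so the censoring is informative and the Kaplan-Meier curve is pushed up. Because other parts of the SAP suggest different handling, two programmers could also produce different event counts from the same data.

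**Working it through.** The plan gives no event rate, missing-visit rate or precision for this endpoint, so there is no stated figure to reproduce. The check applies the rule to visit patterns and then sizes the effect under stated assumptions.

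**1. Patterns.** The boy is able through Week 36 and scores 0 on both days at Week 48.

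| Week 72 | Week 96 | Literal SAP 6.7 | Missed NSAA not counted as a visit | Also using the single day (SAP 7.8) |
|---|---|---|---|---|
| 0, 0 | 0, 0 | Event, Week 48 | Event, Week 48 | Event, Week 48 |
| 0, 0 | Missing, unrelated | Censored, Week 36 | Event, Week 48 | Event, Week 48 |
| 0, 0 | 0 on only day | Censored, Week 36 | Censored, Week 36 | Event, Week 48 |
| Missing, unrelated | 0, 0 | Event, Week 96 | Event, Week 48 | Event, Week 48 |
| 0 on only day | 0, 0 | Event, Week 96 | Event, Week 96 | Event, Week 48 |
| 0, 0 | Missing, task-related | Event, Week 48 | Event, Week 48 | Event, Week 48 |
| 0, 0 | 0 and 1 | Censored, Week 96 | Censored, Week 96 | Censored, Week 96 |

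Rows two to five are the problem. The last row is correct under every reading, because the boy rose on one of the days. A boy who withdraws straight after a two-day zero keeps his event, since no later visit exists.

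**2. Chance that a loss is moved.** Assume each later visit is uninformative with probability m, independently. Suppose the loss is seen at its own visit and k visits follow (k at least 1). Then:

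- dated correctly: (1 − m)^k
- erased: m (the last visit is uninformative)
- delayed: 1 − (1 − m)^k − m

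A loss seen at Week 24 has k = 4 (Weeks 36, 48, 72, 96).

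- m = 5%: 0.95^4 = 81% correct, 5% erased, 14% delayed.
- m = 10%: 0.90^4 = 66% correct, 10% erased, 24% delayed.

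A loss seen at Week 48 has k = 2.

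- m = 5%: 0.95^2 = 90% correct, 5% erased, 5% delayed.
- m = 10%: 0.90^2 = 81% correct, 10% erased, 9% delayed.

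**3. Effect on Kaplan-Meier at Week 96.** Simulation of 200,000 boys per scenario, constant hazard, no dropout, and the SAP's six visits. The reference is the rule of no later ability for unrelated missing visits, and the true simulated proportion for one-day-only visits.

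| Uninformative visits | Assumed true loss | m | Literal | Reference | Overstatement (points) |
|---|---|---|---|---|---|
| Unrelated missing | 20% | 5% | 0.806 | 0.799 | 0.7 |
| Unrelated missing | 20% | 10% | 0.810 | 0.798 | 1.2 |
| Unrelated missing | 35% | 5% | 0.659 | 0.649 | 1.0 |
| Unrelated missing | 35% | 10% | 0.665 | 0.647 | 1.8 |
| Unrelated missing | 50% | 5% | 0.512 | 0.501 | 1.1 |
| Unrelated missing | 50% | 10% | 0.519 | 0.498 | 2.1 |
| One day only | 30% | 5% | 0.711 | 0.699 | 1.2 |
| One day only | 30% | 10% | 0.723 | 0.699 | 2.4 |
| One day only | 50% | 5% | 0.517 | 0.501 | 1.6 |
| One day only | 50% | 10% | 0.532 | 0.500 | 3.2 |

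**4. Scale.** SAP 4.2 plans about 70 treated boys in the 300 to 450 m stratum. If all could rise at baseline, the standard error at Week 96 would be about √(0.7 × 0.3/70) = 5.5 points at 70% able and √(0.5 × 0.5/70) = 6.0 points at 50% able. One boy is 1/70 = 1.4 points.

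**The case against.** The best reply is that the SAP is ambiguous here, not wrong. The qualifier attached to later visits can be read as skipping missed assessments. SAP 7.8 would use a single available day. SAP 6.6 may let an unscheduled assessment within 2 weeks stand in. SAP 6.2.1 scores up to four missing NSAA items as zero, which pushes towards loss. Requiring two zeros is also a sensible way to confirm a first loss. The analysis is descriptive, the shift is about one or two boys, and SAP 7.8.2 also reports the percentage able at each visit without the permanence rule.

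The points on size and on the two-day confirmation stand. The ambiguity does not remove the problem: SAP 6.7 never says which of these rules governs permanence, and the pattern table shows that the event date depends on the choice.

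Three stronger readings might be inferred, and the documents do not support them.

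- **Two zeros are the only route to loss.** They are not; NSAA missing because of inability also counts.
- **Any single-day zero wrongly cancels a loss.** A visit with 0 on one day and 1 or 2 on the other shows ability, so it should break permanence.
- **The same fault reaches LOA and, through it, the 0 m imputation for the 6MWT.** LOA does share a two-day zero ("on 2 consecutive days within a visit or NSAA was not done due to reason related to non-ambulation"), but it has no requirement that every later visit show loss, and tests not done trigger site queries and medical review.

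**Conclusion.** The point holds in limited form. Taken literally, SAP 6.7 lets an uninformative later visit delay an observed loss of rise, or erase it when that visit is the last one. It conflicts with SAP 7.8 on single-day values and departs from the permanence logic that the same section uses for LOA. The error runs one way, towards retained ability.

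Its size is about 1 to 3 percentage points on the Week 96 Kaplan-Meier estimate. That rests on an assumed 5% to 10% of visits being uninformative, independently of each other, a constant hazard and no dropout. It is well inside the sampling error of a group this size. It does not bias a treatment comparison in this SAP, because none is made. It is still worth correcting before database lock: this is a named secondary endpoint, the direction is predictable, and the event date should not depend on the programmer's reading.

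**What to change.** In SAP 6.7, define permanent loss of rise as the first visit showing loss with no later visit having a rise-from-floor score above 0 on any day. State that later visits with NSAA missing for unrelated reasons neither confirm nor cancel it, and that a later zero on the only day tested does not cancel it, in line with SAP 7.8.

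Keep the two-day zero, or task-related missing NSAA, to establish the first loss. If a one-day zero is to be accepted there too, flag losses that rest on a single day at the last visit, since nothing later can check them, and show a sensitivity summary without them. State as well whether the SAP 6.2.1 zero-scoring of missing items and the SAP 6.6 use of unscheduled assessments apply to this endpoint.

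The cost is a few sentences, minor reprogramming and slightly less favourable Kaplan-Meier percentages. Some delay remains when the visit of first loss is itself uninformative: at 5% per visit, of the roughly 5% of losses erased and 10% delayed under the literal rule, about 1% and 4% remain.

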6.8. Programming Conventions

This section details general conventions to be used for the production of tables, figures, and listings. Departures from these general conventions will be specified in appropriate sections.

- For continuous or quantitative variables, mean and median values will be formatted to 1 more decimal place than the measured value on the eCRF. Standard deviation and standard error values will be formatted to 2 more decimal places than the measured value on the eCRF. Minimum and maximum values will be presented with the same number of decimal places as the measured value on the eCRF. Percentages will be presented with 1 decimal place.
- For categorical variables, the number and percentage of a category will be presented in the form XX (YY%), where the percentage is YY.
- Study Day will appear in the data listings as appropriate.
- Date variables will be formatted as DDMMYY YYYY for presentation. In the case of missing day, month, and/or year information, “UN”, “UNK”, or “UNKN” will be presented. For example, a date with a missing month and day will be presented as UNUNKYYYY.
- SAS® Version 9.4 or higher will be the statistical software package used for all analyses unless otherwise specified.
- R version 3.2.2 or higher and DAAG package 1.22 or higher will be used for the one-sample permutation test.
- The CDISC Study Data Tabulation Model Implementation Guide (SDTMIG) V3.2 for preparing data set will be used for this study.
- Tables, figures, and listings will be presented in landscape orientation.
- Listings will be sorted by treatment group, patient, and then date, unless otherwise specified.

7. STATISTICAL ANALYSES

7.1. Patient Disposition

Patient disposition will be summarized by treatment group for all patients enrolled and will include the frequency count and percentage for the following items: patients in the Safety Set, patients in the efficacy set, patients in the primary efficacy set, patients in the efficacy set with Baseline 6MWT > 450, patients who were randomized to a second biopsy (eteplirsen-treated patients only), patients who were treated, patients who completed the Week 96 efficacy visit, patients who completed the study, and patients who discontinued early. The reasons for discontinuation will also be summarized. Descriptive statistics will be presented for weeks on study.

An additional summary will be produced for the primary efficacy set.

Patient disposition and patient eligibility will be presented in data listings.

7.2. Demographics and Baseline Characteristics

Demographic and baseline characteristics will be summarized by treatment group for the safety set. These variables will include age (years), race, ethnicity, Baseline height (cm), Baseline weight (kg), Baseline body mass index (kg/m²), time since DMD diagnosis (months) at Baseline, mutation type(s), previous drisapersen exposure status, corticosteroid medication, corticosteroid schedule, duration of prior corticosteroid use at Baseline, prior physiotherapeutic interventions (within 3 months prior to the study: Yes vs No), and Baseline 6MWT distance.

An additional summary will be produced for the primary efficacy set and for the subset of patients with Baseline 6MWT > 450 meters.

Patient-level demographic data and baseline characteristics will be presented in data listings.

7.3. Prior and Concomitant Medications

Concomitant medications will be coded by Preferred Term (PT) using the World Health Organization (WHO) Drug Dictionary (WHODRUG, 01DEC2013). The number and percentage of patients in the Safety Set taking concomitant medications will be tabulated by Anatomical Therapeutic Chemical classification pharmacological subgroup and WHO drug PT by treatment group. At each level of summarization, a patient is counted once if he reported 1 or more medications at that level.

All medications, whether prior or concomitant, will be presented in data listings. Separate listings of glucocorticoids and prior experimental DMD drugs will be presented.

7.4. Medical History

Medical history data for the Safety Set will be presented in data listings.

7.5. Physiotherapeutic Interventions

Physiotherapeutic interventions will be presented in data listings.

7.6. Protocol Deviations

A listing of major protocol deviations will be provided. The major protocol deviations will be identified based on a review of the study data prior to the lock of the database and will include the nature of the deviation (eg inclusion/exclusion, prohibited therapies). Additionally, major deviations will be summarized by deviation type.

7.7. Exposure to Study Drug

The exposure to eteplirsen will be summarized for eteplirsen-treated patients in the Safety Set. The variables will include the following (as applicable): cumulative exposure administered (mg), number of infusions of treatment, and duration on eteplirsen (weeks). Additionally, duration on eteplirsen category will be summarized for the following intervals: < 24 weeks, 24 to < 48 weeks, 48 to < 72 weeks, 72 to < 96 weeks, and \geq 96 weeks.

Patient-level study drug information will be provided in a data listing. Additionally, a listing of the derived exposure parameters listed above will be generated as well as a listing of overdoses. The actual dose will be compared to the planned dose (Section 6.7). Any actual dose that is greater than 1.10 times the planned dose will be considered an overdose. Planned dose is calculated as the dose level in mg/kg multiplied by the patient's most recent weight prior to the dose (or on the same day with no time).

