9.3.2. Administration of the Investigational Product

The dose of eteplirsen will be calculated based on the most recent patient weight obtained at the site prior to the current visit. Eteplirsen should be prepared for dosing by following the steps detailed in the study specific Pharmacy Manual.

Eteplirsen will be administered as an IV infusion over a period of approximately 35 to 60 minutes. It is recommended that a topical anesthetic cream (e.g., lidocaine 2.5%, prilocaine 2.5%, or LMX4 cream) be applied to the infusion site prior to each administration of eteplirsen.

An implanted venous access port may be inserted for eteplirsen administration at the discretion of the Investigator. If eteplirsen is administered into an existing IV line, the line should be flushed with normal saline before and after administration of eteplirsen. After eteplirsen administration and the saline flush, the port may be flushed with heparin to heplock the port prior to removal of the infusion line.

No other medications may be administered concomitantly during the eteplirsen infusion.

All treated patients will be observed for at least 1 hour following the end of each eteplirsen infusion.

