10.2. Study Assessments by Visit

Assessments of AEs and concomitant medications will be performed at every study visit. Various study assessments may be performed at different sites.

A 'Local Site' will be the site a patient most frequently visits for infusions and routine assessments. All assessments scheduled on the same day as eteplirsen administration are to be completed prior to initiation of eteplirsen infusion, except for postdose blood draws for PK as indicated in Section 2.

A 'Hub Site' will perform functional efficacy and cardiac assessments. Patients enrolled at certain Local Sites will therefore need to travel to a Hub Site. A Hub Site may also be a particular patient's Local Site. Hub Sites have been introduced to minimize the number of clinical evaluators and thereby reduce rater-dependent variability in the study cohort. Each Hub Site will have at least 2 expert clinical evaluators who will have undergone standardized training and have been certified to be capable of performing all clinical assessments as specified for this study. To further reduce variability, every effort should be made to have each patient assessed by the same clinical evaluator for each specific assessment throughout the entire study; all assessments will be done in the same order as listed in the Clinical Evaluator Manual, at approximately the same time of day, and clinical evaluators will not have access to prior test results or information related to study-specific or routine patient care. Efficacy evaluations will be performed in the morning and cardiac assessments will be performed after completion of the functional assessments, at a consistent time of day for each visit during the course of the study.

To reduce the burden on the untreated control patients, all protocol-specified assessments after Week 12 may be performed at the Hub Site (Table 5). If a patient transfers to their assigned Hub Site for collection of safety assessments (e.g., laboratory assessments, vital signs, and physical examinations), the functional assessments must be done first, and the safety assessments should be done after completion of the functional assessments.

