10.2.3. Weekly Infusions (Weeks 1-96) (for the treated group only)

At Local Sites:

- Vital signs, including include blood pressure, heart rate, respiration, and oral temperature. Vital signs will be measured 30 minutes prior to the start of the infusion and 5, 30, and 60 minutes after the end of the infusion. If the patient has not experienced an infusion reaction after the first year of treatment, vital signs may be reduced to pre-infusion and 30 minutes after the end of the infusion. Vital signs should be collected as close to or at the exact indicated times as possible.
- Eteplirsen will be administered via an IV infusion. Patients should be closely monitored for at least 1 hour following the completion of all infusions. It is recommended that a topical anesthetic cream (e.g., lidocaine 2.5%, prilocaine 2.5% or LMX4 cream) be applied prior to infusions. Refer to the Pharmacy Manual for specific instructions regarding IP reconstitution with normal saline.

10.2.4. Additional Procedures for Week 1

The assessments below should occur during a single day at a patient's Local Site.

- Full physical examination, including examination of general appearance, HEENT, heart, chest, abdomen, skin, lymph nodes, extremities, musculoskeletal, and neurological systems
- Vital signs
- Weight (This measurement will be used to calculate the eteplirsen dose for patients in the treated group.)
- Safety laboratory assessments, including chemistry, hematology, coagulation, and urinalysis
- Immunogenicity
- At a subset of sites for patients in the treated group, 1 blood sample for assessing plasma drug concentrations (PK) will be taken within 2 hours prior to the start of the first infusion of eteplirsen.

10.2.5. Additional Procedures for Week 4

Assessments should occur during a single day at the patient's Local Site.

- Full physical examination, including examination of general appearance, HEENT, heart, chest, abdomen, skin, lymph nodes, extremities, musculoskeletal, and neurological systems
- Vital signs
- Weight
- Safety laboratory assessments, including chemistry, hematology, coagulation, and urinalysis
- Immunogenicity

10.2.6. Additional Procedures for Week 8

Assessments should occur during a single day at the patient's Local Site.

- Brief physical examination, including examination of general appearance, HEENT, heart, chest, abdomen, and skin
- Vital signs

- Weight
- Safety laboratory assessments, including chemistry, hematology, coagulation, and urinalysis

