10.2.11. Safety Extension (Not to Exceed 48 Weeks)

Patients in the treated group may continue on in the safety extension for a period not to exceed 48 weeks, until the product is commercially available or until they can transition into a separate eteplirsen study.

During the safety extension, patients will continue to receive 30 mg/kg/week eteplirsen as an IV infusion, and will undergo physical examinations and assessments of safety laboratory parameters, weight, AEs and concomitant medications as specified in Table 4.

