6.7. Definitions and Terminology

Day 1

Day 1 will be defined as the date of the first eteplirsen dosing for eteplirsen-treated patients, or the Week 1 visit date for untreated control patients.

Study Day

Study day will be defined as Event Date – Day 1 + 1.

Duration on Study

Duration on study will be calculated as the duration in weeks from Day 1 to the date of study completion/discontinuation as recorded on the END OF STUDY eCRF (if completed) or the date of the last study assessment or procedure.

Duration on Eteplirsen

Duration on eteplirsen will be calculated as the duration in weeks from Day 1 to the date of the last eteplirsen administration as recorded on the STUDY DRUG ADMINISTRATION eCRF plus 6 days (ie, [last dose – first dose date + 1 + 6]/7).

Duration in weeks calculated above will be then categorized to 1 of the following intervals: <24, 24 to <48, 48 to <72, 72 to <96, or ≥ 96 .

Planned Dose and Overdose

The body weight-based planned dose was calculated based on most recent weight of previous visits. When calculating the planned dose, the body weight is rounded to a single decimal using conventional rounding rules. While in preparing actual dose, an unconventional rule is applied for calculating the volume of the concentrated drug (50 mg/mL) in milliliter. Any volume of 0.1 or above is rounded up (eg 25.14 mL is rounded up to 26 mL) and any volume below 0.1 is rounded down (eg 25.09 mL is round up to 25 mL). The overdose is defined as any actual dose $>10\%$ above the planned body weight-based dose.

Baseline Visit and Baseline value

Baseline visit will be considered the last visit prior to the initiation of eteplirsen for eteplirsen-treated patients, or the last visit on or before the Week 1 visit for untreated control patients. For any assessment that is taken on 2 consecutive days at baseline visit the base visit (ie, 6MWT, NSAA items and total score, FVC % predicted), the average value will be considered as the baseline value. If the assessment is taken or available only on 1 day at baseline visit, then the value on that day will be used as baseline value.

Change from Baseline

Change from Baseline will be calculated as follows:

$$\text{Change from Baseline} = \text{Post-Baseline Value} - \text{Baseline Value}$$

Percent Change from Baseline

Percent change from Baseline will be calculated as follows:

$$\text{Percent change from Baseline} = (\text{Change from Baseline} / \text{Baseline Value}) * 100$$

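### SAP 7.7 points to Section 6.7 for the planned dose, then redefines it with a different body weight, so the overdose listing depends on which sentence is programmed

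*SAP*

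**What the plan says.** SAP 6.7 (Planned Dose and Overdose) states: "The body weight-based planned dose was calculated based on most recent weight of previous visits". It rounds that weight to one decimal. It then gives the volume rule for preparing the 50 mg/mL concentrate: "Any volume of 0.1 or above is rounded up", and smaller fractions are dropped. An overdose is any actual dose more than 10% above the planned dose.

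SAP 7.7 (Exposure to Study Drug) promises a listing of overdoses and says "The actual dose will be compared to the planned dose (Section 6.7"). It repeats the 1.10 threshold, then defines the planned dose as the mg/kg level multiplied by the patient's "most recent weight prior to the dose (or on the same day with no time").

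Three protocol statements bear on which weight is used:

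- Protocol 9.3.2, the general dosing rule: "The dose of eteplirsen will be calculated based on the most recent patient weight obtained at the site prior to the current visit".
- Protocol 10.2.4, on the Week 1 weight: "This measurement will be used to calculate the eteplirsen dose for patients in the treated group".
- Protocol 10.2, on the order of events: "All assessments scheduled on the same day as eteplirsen administration are to be completed prior to initiation of eteplirsen infusion".

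I read 9.3.2 and 10.2.4 as a general rule with a Week 1 exception, not as a conflict.

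**The concern.** A weight taken at the dosing visit is excluded by 6.7 and admitted by 7.7. Because Protocol 10.2 puts same-day assessments before the infusion, a scheduled dosing-day weight always qualifies under 7.7. The same SAP paragraph therefore gives a programmer two instructions.

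Choosing either existing sentence does not solve it. Section 6.7 misses the first dose, which is prepared on the Week 1 weight. Section 7.7 misses later doses at weight visits, which are prepared on an earlier weight. So there are two routes to a false entry:

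- under 7.7, a later dose after weight loss since the previous weighing;
- under 6.7, the Week 1 dose after weight gain since Screening.

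Rounding the volume up usually consumes part of the 10% margin, so the weight change needed is usually below 10%. At stake is whether the overdose listing, a named safety output in a paediatric trial, is reproducible and labels only genuine departures from the dosing rule.

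**Working it through.** **Inputs.** Dose 30 mg/kg; concentrate 50 mg/mL; weight to 0.1 kg; a fraction of 0.1 mL or more rounds up; threshold 1.10 (SAP 4.1, 6.7, 7.7). Weight schedule from Protocol Tables 2 and 3. The documents give no body weights, so the weight bands and percentage changes below are assumptions.

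**The plan's own figures.** The rounding rule reproduces the SAP 6.7 examples: 25.14 mL becomes 26 mL and 25.09 mL becomes 25 mL.

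**Formulas.** Volume = 30 × weight / 50 = 0.6 mL/kg, rounded as above. Actual dose = 50 mg × rounded mL. Ratio = actual dose / (30 × comparison weight). The dose is listed if the ratio exceeds 1.10.

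**Where the rules differ.** Weight is scheduled at Week 1 and every 4 weeks from Week 4 to Week 96: 1 + 24 = 25 of 96 infusions, taking weight and infusion to fall on the same day. At other infusions the rules agree. Weight is also collected in the safety extension (Protocol 10.2.11: "assessments of safety laboratory parameters, weight, AEs and concomitant medications as specified in Table 4"). The weight row of Table 4 is broken in the text available to me. If it is every 4 weeks, Weeks 100 to 144 add 12, giving 37 of 144.

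**Two correctly prepared doses.**

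| | Previous weight | Same-day weight | Dose prepared | Ratio, 6.7 | Ratio, 7.7 |
|---|---|---|---|---|---|
| Later visit | 25.2 kg | 24.2 kg | 15.12 → 16 mL = 800 mg | 800/756 = 1.058, not listed | 800/726 = 1.102, listed |
| Week 1 | 24.0 kg | 25.2 kg | 15.12 → 16 mL = 800 mg | 800/720 = 1.111, listed | 800/756 = 1.058, not listed |

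**Rounding is not the cause by itself.** With one weight for both dosing and comparison, 0 of 450 grid weights from 15.0 to 59.9 kg are listed. From 18 kg upwards, rounding takes at most 8.1% of the 10% margin (18.5 kg: 11.1 → 12 mL; 600/555 = 1.081).

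**Later doses with 7.7 programmed.** Grid weights falsely listed after a given loss since the previous weighing:

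| Loss | 18–25 kg | 25–35 kg | 35–50 kg | 50–70 kg |
|---|---|---|---|---|
| 1% | 0/71 | 0/101 | 0/151 | 0/201 |
| 3% | 5/71 | 0/101 | 0/151 | 0/201 |
| 5% | 22/71 | 12/101 | 0/151 | 0/201 |
| 7% | 41/71 | 50/101 | 48/151 | 17/201 |

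The smallest loss that triggers a listing has a median of 6.7% (range 2.2–10.1%), 7.2% (4.0–9.7%), 7.8% (5.4–9.6%) and 8.1% (6.6–9.5%) in the four bands. The minimum is at 18.5 kg: 600 mg is listed at 18.1 kg (600/543 = 1.105), a loss of 0.4 kg.

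**Week 1 with 6.7 programmed.** Dose on the Week 1 weight w, comparison weight w / (1 + gain). A 3% gain lists 3/71 at 18–25 kg and none above. A 5% gain lists 20/71, 7/101, 0/151 and 0/201.

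**The case against.** The best defence is that the 6.7 sentence is in the past tense and sits beside text on dose preparation. It could describe how sites dosed, leaving 7.7 as the programming rule and only a loose cross-reference to tidy. That fails because 7.7 itself sends the comparison to the planned dose of 6.7. Even on that reading, 7.7 would compare later doses with a weight that sites were told not to use.

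The objections on size carry more weight:

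- **Direction.** These are growing boys on corticosteroids. When weight rises after the previous weighing, the 7.7 ratio falls: over 18–70 kg, gains of 1%, 3% and 5% give no false listing. The loss table describes the less usual direction. Weighings are about 4 weeks apart, and SAP Appendix Table 4 already treats a 7% loss from Baseline as markedly abnormal, so losses of 5% or more between weighings should be uncommon.
- **Reach.** The gain route under 6.7 touches one infusion per patient.
- **The 25 of 96.** It counts where the rules can pick different weighings, not where a listing changes. The protocol states single-day assessments explicitly only for Weeks 1, 4 and 8; for the other visits, a same-day weight and infusion is inferred from the schedule.
- **Rounding.** Fractions below 0.1 mL round down, so a change below 10% is not always enough: one of the 71 weights at 18–25 kg needs 10.1%.
- **Consequence.** Patient-level dosing data are listed as well, so a reader could check an entry.

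All of these stand as limits on size. None removes the contradiction.

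**Conclusion.** The concern holds as a minor inconsistency, with high confidence. The SAP gives two planned-dose definitions that use different weights at scheduled weight visits, and neither follows the protocol's dosing rule at every infusion. The same compliant dose can be listed or not depending on the sentence programmed.

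The practical effect falls mainly on the lightest boys. Grid counts are shares of assumed weights, not of patients, and nothing in the documents shows how many boys fall in the 18–25 kg band. The damage is confined to the descriptive overdose listing. No efficacy analysis is touched, nor is the protocol's overdose reporting, which uses a separate limit of 50 mg/kg (Protocol 11.6.1).

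**What to change.** Keep one planned-dose definition, in SAP 6.7, tied to the weight used for dosing:

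- first dose: the Week 1 weight (Protocol 10.2.4);
- all later doses, including the safety extension: the most recent weight from a previous visit (Protocol 9.3.2), rounded to one decimal as now.

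Delete the second definition from SAP 7.7 and let 7.7 refer to 6.7 only. A cross-reference from Protocol 9.3.2 to 10.2.4 would help but is optional.

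The cost is one SAP sentence revised and one deleted, using weights already collected. It needs no protocol amendment, no new data and no change to any infusion.
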